5.6 Follow-Up for Subject Withdrawal from Study

Discontinuation of Study Drug and Continuation of Study Participation

If a subject prematurely discontinues study drug, the procedures outlined for a Premature Discontinuation Visit (PD Visit) should be completed as soon as possible, preferably within 2 weeks, and preferably prior to initiation of another therapy. To minimize missing data for efficacy and safety assessments, subjects who prematurely discontinue study drug treatment should continue to be followed for all regularly scheduled visits as outlined in the Activity Schedule ([Appendix D](#)) and adhere to all study procedures except for dispensing study drug, PK sample collection, and blood sample collection for optional biomarker research studies, unless subjects have decided to discontinue study participation entirely (withdrawal of informed consent). In addition, all efficacy-driven criteria for addition or modification of background medications and study drug discontinuation no longer apply. If at any point a subject no longer wants to provide assessments (withdrawal of informed consent) following discontinuation of study drug, a second PD Visit is not required. Subjects should be advised on the continued scientific importance of their data even if they discontinue treatment with study drug early. Following discontinuation of study drug, the subject should be treated in accordance with the Investigator's best clinical judgment irrespective of whether the subject decides to continue participation in a study.

Premature Discontinuation of Study (Withdrawal of Informed Consent)

If a subject prematurely discontinues study participation (withdrawal of informed consent), the procedures outlined for the PD Visit should be completed as soon as possible, preferably within 2 weeks, and preferably prior to initiation of another therapy. In addition, if subject is willing, a 30-day F/U Visit (or phone call) after the last dose of study drug may be completed to determine the status of any ongoing AEs/SAEs or the occurrence of any new AEs/SAEs.

For subjects to be considered lost to follow-up, reasonable attempts must be made to obtain information on the subject's final status. At a minimum, 2 telephone calls must be made and 1 certified letter must be sent and documented in the subject's source documentation.

5.7 Study Drug

Study drugs refer to drugs that are used (or can be used) in this study to assess the safety and the efficacy of the Investigational Product. Investigators will assess the relationship of AEs to the use of study drugs.

Study drug will be taken orally QD, beginning on Day 1 (Baseline), and should be taken at approximately the same time each day, with or without food. Subjects will be instructed to return all drug containers (even if empty) to the study site personnel at each study visit; study site personnel will document compliance.

Subjects will continue their disease-related concomitant medications therapy as allowed per protocol. AbbVie will not supply any disease-related concomitant medication therapy taken during the course of each study.

AbbVie will supply upadacitinib and matching upadacitinib placebo.

All study drug investigational product must be stored at controlled room temperature (15° to 25°C/59° to 77°F). Study drug will be packaged in quantities sufficient to accommodate study design.

Each kit will be labeled per local requirements and this label must remain affixed to the kit. Upon receipt, study drug should be stored as specified on the label and kept in a secure location. Each kit will contain a unique kit number. This kit number is assigned to a subject via interactive response technology (IRT) and encodes the appropriate study drug to be dispensed at the subject's corresponding study visit. All blank spaces on the label will be completed by the site staff prior to dispensing to subjects. Study drug will only be used for the conduct of the study.

The individual study drug information is presented in [Table 2](#).

Table 2. Description of Study Drug

Investigational Product	Mode of Administration	Dosage Form	Strength	Blinded or Open Label	Frequency	Manufacturer
Upadacitinib (ABT-494)	Oral	Film-coated tablets	15 mg	Blinded for Double-Blind Period; unblinded for Open-Label Extension Period ^a	QD	AbbVie
Placebo for upadacitinib (ABT-494)	Oral	Film-coated tablets	Not applicable	Blinded for Double-Blind Period ^a	QD	AbbVie

a. For Study 1 and Study 2, study sites and subjects will remain blinded to the Double-Blind Period treatment assignments for the duration of the respective study.

If a subject is unable to come to the study site to pick up their study drug due to COVID-19, a direct-to-patient (DTP), study drug shipment can be made from the study site to the subject if allowed by local regulations. AbbVie will submit any required notifications to the regulatory authority as applicable. Refer to the Operations Manual in [Appendix G](#) for details on DTP shipment of study drug.

5.8 Randomization/Drug Assignment and Blinding

All subjects will be assigned a unique identification number by the IRT at the screening visit. For subjects who re-screen, the screening number assigned by the IRT at the initial screening visit should be used. The IRT will assign a randomization number that will encode the subject's treatment group assignment according to the randomization schedule generated by the statistics department at AbbVie. In the Double-Blind Period, subjects will be randomized in a 1:1 ratio to 1 of 2 treatment groups:

Study 1 (bDMARD-IR AS):

- Group 1: Upadacitinib 15 mg QD (N = 193)

- Group 2: Placebo QD (N = 193)

Study 2 (nr-axSpA):

- Group 1: Upadacitinib 15 mg QD (N = 152)
- Group 2: Placebo QD (N = 152)

In Study 1 (bDMARD-IR AS), randomization will be stratified by hsCRP (\leq ULN versus $>$ ULN) collected at Screening Visit, the class of the prior bDMARD use (1 TNF inhibitor, 1 IL-17 inhibitor, and "other"), and geographic region (US/Canada versus Rest of the World excluding Japan and China). The "other" category of prior bDMARD use includes exposure to 2 bDMARDs and cannot exceed 30% of subjects. Japan and China will each have a separate randomization schedule stratified by hsCRP (\leq ULN versus $>$ ULN) collected at Screening Visit.

In Study 2 (nr-axSpA), randomization will be stratified by MRI and screening hsCRP status (MRI+/hsCRP $>$ ULN, MRI+/hsCRP \leq ULN, and MRI-/hsCRP $>$ ULN) and exposure to bDMARDs (yes versus no). At least 20%, but not exceeding 35% of subjects with prior exposure to a bDMARD will be enrolled in Study 2. Japan and China will each have a separate randomization schedule stratified by MRI and screening hsCRP status (MRI+/hsCRP $>$ ULN, MRI+/hsCRP \leq ULN, and MRI-/hsCRP $>$ ULN).

Subjects in the placebo group will be switched to upadacitinib 15 mg QD at Week 14 in the Open-Label Extension Period for Study 1 (bDMARD-IR AS) and Week 52 in the Open-Label Extension Period for Study 2 (nr-axSpA).

All AbbVie personnel with direct oversight of the conduct and management of the trial (with the exception of AbbVie Drug Supply Management Team), the Investigator, study site personnel, and the subject will remain blinded to each subject's treatment until the Week 14 primary analysis for Study 1 (bDMARD-IR AS). For Study 2 (nr-axSpA), all AbbVie personnel with direct oversight of the conduct and management of the trial (with the exception of AbbVie Drug Supply Management Team) will remain blinded to each subject's treatment until the Week 14 primary analysis, while the Investigator, study site personnel, and the subject will remain blinded to each subject's treatment until after all subjects have completed the Week 52 visit or have prematurely discontinued prior to Week 52. For Study 1 and Study 2, sites and subjects will remain blinded to the Double-Blind Period treatment assignments for the duration of the respective study. To maintain the blind, the upadacitinib tablets and placebo tablets provided for each study will be identical in appearance. The IRT will provide access to unblinded subject treatment information in the case of a medical emergency.

In the event of a medical emergency that requires unblinding of the study drug assignment, the Investigator is requested to contact the AbbVie TA MD prior to breaking the blind. However, if an urgent therapeutic intervention is necessary which warrants breaking the blind prior to contacting the AbbVie TA MD, the Investigator can directly access the IRT system to break the blind without AbbVie notification or agreement. Unblinding is available in the IRT system via the Unblind Subject transaction, which is available only to the Investigator. If the IRT system is unavailable, unblinding may occur by contacting the technical support of the IRT vendor via either phone (preferred) or email ([contact]). For country-specific phone numbers, please see the following website: <http://www.endpointclinical.com/helpdesk/>.

In the event that the blind is broken before notification to the AbbVie TA MD, we request that the AbbVie TA MD be notified within 24 hours of the blind being broken. The date and reason that the blind was broken must be conveyed to AbbVie and recorded on appropriate eCRF.

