3.3 Secondary Endpoints

Study 1 (bDMARD-IR AS):

The multiplicity-controlled secondary endpoints at Week 14 are:

1. Change from Baseline in Ankylosing Spondylitis Disease Activity Score (ASDAS);
2. Change from Baseline in magnetic resonance imaging (MRI) Spondyloarthritis Research Consortium of Canada (SPARCC) score (spine);
3. Bath Ankylosing Spondylitis Disease Activity Index (BASDAI) 50 response;
4. ASAS20 response;
5. ASDAS Inactive Disease (ID) (ASDAS score < 1.3);
6. Change from Baseline in Patient's Assessment of Total Back Pain (Total Back Pain);
7. Change from Baseline in Patient's Assessment of Nocturnal Back Pain (Nocturnal Back Pain);
8. ASDAS LDA (ASDAS score < 2.1);
9. Change from Baseline in Bath Ankylosing Spondylitis Functional Index (BASFI);
10. ASAS partial remission (PR) (an absolute score of ≤ 2 units for each of the 4 domains identified in ASAS40);
11. Change from Baseline in Ankylosing Spondylitis Quality of Life (ASQoL);

12. Change from Baseline in ASAS Health Index (HI);
13. Change from Baseline in Linear Bath Ankylosing Spondylitis Metrology Index (BASMI_{lin});
14. Change from Baseline in Maastricht Ankylosing Spondylitis Enthesitis Score (MASES).

Additional secondary endpoint at Week 14:

- Change from Baseline in MRI SPARCC score (SI joints).

Study 2 (nr-axSpA):

The multiplicity-controlled secondary endpoints at Week 14 (unless otherwise noted) are:

1. Change from Baseline in ASDAS;
2. Change from Baseline in MRI SPARCC score (SI joints);
3. BASDAI 50 response;
4. ASDAS ID (ASDAS score < 1.3);
5. Change from Baseline in Patient's Assessment of Total Back Pain (Total Back Pain);
6. Change from Baseline in Patient's Assessment of Nocturnal Back Pain (Nocturnal Back Pain);
7. ASDAS LDA (ASDAS score < 2.1);
8. ASAS PR (an absolute score of ≤ 2 units for each of the 4 domains identified in ASAS40);
9. Change from Baseline in BASFI;
10. Change from Baseline in ASQoL;
11. Change from Baseline in ASAS HI;
12. ASAS20 response;
13. Change from Baseline in BASMI_{lin};
14. Change from Baseline in MASES;
15. ASAS40 response at Week 52 (for European Union [EU]/European Medicines Agency [EMA] regulatory purposes).

For US/Food and Drug Administration (FDA) regulatory purposes, the last multiplicity-controlled secondary endpoint is change from Baseline in MASES.

Additional secondary endpoints are:

- Change from Baseline in MRI SPARCC score (spine) at Week 14;
- Initiation of rescue between Week 24 and Week 52;

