The AbbVie study team will be unblinded to perform the Week 14 primary analysis for both studies. Reporting will be performed independently for Study 1 and Study 2. For Study 1 and Study 2, the unblinding will take place after all subjects in the study have completed the Week 14 visit or have prematurely discontinued prior to Week 14. For both Study 1 and Study 2, sites and subjects will remain blinded to the Double-Blind Period treatment assignments for the duration of the study.

Information on the Data Monitoring Committee (DMC) and Cardiovascular Adjudication Committee (CAC) are described in Section 6.3 and Section 6.1, respectively.

See Section 5 for information regarding eligibility criteria and Section 5.8 for information on stratification.

The schematic of Study 1 and Study 2 is shown in Figure 1. Further details regarding study procedures are located in the operations manual (Appendix G).

For subjects in Japan only: Upon marketing approval of upadacitinib for the treatment of nr-axSpA in Japan, M19-944 Study 1 and Study 2 will be changed from Phase 3 studies to post-marketing clinical studies in Japan.

Remission-Withdrawal Period

[figure not shown]
Subjects in Study M19-944 from both Study 1 (AS bDMARD-IR) and Study 2 (nr-axSpA) who reach Week 104 on study drug (upadacitinib 15 mg QD) will be assessed whether they are in remission, with an ASDAS (CRP) < 1.3 at Week 104 and an ASDAS (CRP) < 2.1 at Week 88.

Subjects in remission at Week 104 will be eligible for the Remission-Withdrawal Period. Subjects will be followed without study drug treatment and assessed for disease flare through Week 152. Flare is defined as an ASDAS (CRP) \geq 2.1 at 2 consecutive visits, which are at least 2 weeks apart, or an ASDAS (CRP) > 3.5 at one visit. Subjects who flare will receive open-label upadacitinib 15 mg QD from the time of flare for 24 weeks (re-treatment) or longer per local country requirements (See Appendix F for more details).

Subjects who do not flare, will be followed without upadacitinib treatment until Week 152.

Subjects who are not in remission at Week 104 will complete the study after the 30 day follow-up visit OR, if applicable, will have the option to enter open-label treatment with upadacitinib until a predefined time period only per local country requirements (See Appendix F).

Figure 1. Study Schematic

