5.5 Withdrawal of Subjects and Discontinuation of Study

AbbVie may terminate Study 1 and/or Study 2 and/or the Remission-Withdrawal Period prematurely, either in its entirety or at any site. Study 1 and/or Study 2 and/or the Remission-Withdrawal Period will be discontinued or terminated in case of an unacceptable risk, any relevant toxicity, or a negative change in the benefit:risk assessment. This might include the occurrence of AEs with a character, severity, or frequency that is new in comparison to the existing risk profile. In addition, data deriving from other clinical trials or toxicological studies which negatively influence the benefit:risk assessment might cause discontinuation or termination of a study. The Investigator may also stop a study at their site if they have safety concerns. If AbbVie terminates a study for safety reasons, AbbVie will promptly notify the Investigator. Advance notice is not required by either party if a study is stopped due to safety concerns.

Subjects can request to be discontinued from participating in a study at any time for any reason. The Investigator may discontinue any subject's participation at any time for any reason. The AbbVie TA MD/Scientific Director may mandate individual subject discontinuation from study drug in case of safety concern.

For each study, subjects must have study drug discontinued immediately if any of the following occur:

- The subject requests withdrawal from the study.
- The Investigator believes it is in the best interest of the subject.
- Abnormal laboratory results or AEs that either meet the criteria for discontinuation of study drug as stated in Section 6.2 or as determined by the Investigator or the AbbVie TA MD, that rule out safe continuation of the study drug.
- Serious infections (e.g., sepsis) which cannot be adequately controlled by anti-infective treatment or would put the subject at risk for continuation of the study drug.
- Subject is non-compliant with TB prophylaxis (if applicable) or develops active TB at any time during the study.
- Malignancy, except for localized NMSC or carcinoma in situ of the cervix.
- Subject develops a GI perforation (defined as acute, spontaneous perforation of the GI tract that requires inpatient medical care or urgent surgical intervention other than appendicitis or mechanical injury). See also Section 6.2 Toxicity Management.

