6.3 Data Monitoring Committee

For each study, an independent, external DMC will be established for periodic review of unblinded safety data and to alert AbbVie to possible safety concerns related to the conduct of the study to ensure subject safety. If necessary to ensure subject safety, the DMC will also be given access to selected efficacy data which will be specified in the DMC charter.

The DMC charter will describe the roles and responsibilities of the DMC members, frequency of data reviews, and relevant data to be assessed. Communications from the DMC to the Study Team will not contain information that could potentially unblind the team to subject treatment assignments.

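### Study 2: sponsor conduct staff lose the subject-level blind at the Week 14 analysis, although the placebo-controlled period and the last EU/EMA-controlled endpoint run to Week 52

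*Protocol*

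**What the plan says.** **Sponsor blind.** For Study 2, Protocol Section 5.8 says that sponsor personnel with direct oversight of conduct and management (drug supply excepted) stay blind to individual assignments "until the Week 14 primary analysis, while the Investigator, study site personnel, and the subject will remain blinded" until every subject has passed or left before Week 52. Section 4.1 says: "The AbbVie study team will be unblinded to perform the Week 14 primary analysis for both studies". The trigger is that "the unblinding will take place after all subjects in the study have completed the Week 14 visit" or has discontinued earlier; Section 7.1 ties the database lock to the same event.

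**Site and subject blind.** Section 5.8 gives two end-points in each study. In Study 1 the site blind lasts until the Week 14 primary analysis; in Study 2 it lasts until all subjects are through Week 52. The same paragraph then says that "sites and subjects will remain blinded to the Double-Blind Period treatment assignments for the duration of the respective study". Section 4.1, the footnote to Table 2 in Section 5.7, and Section 7.1 give only this last version.

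**Endpoint.** Item 15 of the controlled Study 2 list in Section 3.3 is "ASAS40 response at Week 52 (for European Union [EU]/European Medicines Agency [EMA] regulatory purposes". Section 7.6 places it at the end of the fixed sequence for EU/EMA; the FDA sequence stops one step earlier, at change in MASES. For binary endpoints in the placebo-controlled period up to Week 52, Section 7.3 counts a subject as a non-responder at visits after stopping study drug or starting rescue.

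**The concern.** A double-blind period is normally protected on both sides: those who give and receive treatment, and those at the sponsor who manage subjects, answer site questions and query data. In Study 2 the second protection ends, on the protocol's wording, when the last subject passes Week 14. Later enrollees then still have up to 38 weeks of placebo-controlled follow-up.

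During those weeks the sponsor's Therapeutic Area Medical Director (TA MD) or Scientific Director "may mandate individual subject discontinuation from study drug in case of safety concern", and the TA MD is consulted on other individual questions. Because stopping study drug or using rescue is itself a component of the Week 52 outcome, a sponsor decision or piece of advice given with knowledge of treatment could alter a controlled endpoint. Even if none did, the Week 52 comparison could not be described as coming from a period in which those running the trial were blinded to individual assignments.

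**Working it through.** **1. The plan's own figures.** The point rests on no sample-size figure. The nearest one holds: Section 7.7 claims at least 90% power for Week 14 ASAS40 with 304 subjects, 42% versus 17%, two-sided 0.05 and 10% dropout. With 152 × 0.9 ≈ 136 per arm, a two-sided test of two proportions gives power of 99.6%. The claim of at least 80% for Week 52 ASAS40 cannot be reproduced, because no Week 52 rates are given.

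**2. What is exposed.** All Week 14 visits are complete before unblinding. The primary endpoint and the 14 controlled Week 14 secondaries therefore precede it, and with them the whole FDA sequence. The only controlled endpoint left open is Week 52 ASAS40.

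**3. Sponsor routes into an individual's Week 52 outcome.**

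| Provision | What it allows | Bears on Week 52 ASAS40? |
|---|---|---|
| 5.5 | TA MD/Scientific Director may require a subject to stop study drug, for safety only | Yes |
| 6.2, major cardiovascular event | Investigator discusses continuing study drug with the TA MD | Yes |
| 5.4 | Concomitant-therapy questions go to the TA MD or the sponsor's emergency contact | Possibly, through advice |
| 5.4, rescue | Written rule on ASAS20 non-response at two consecutive visits; investigator or site staff determine the response | Trigger is in blinded hands |
| Table 3, ALT/AST > 8 × ULN | Interrupt, confirm, contact the TA MD; the restart and discontinuation criteria give the TA MD no decision | No stated decision |
| 5.10, annual TB seroconversion | Scheduled tests fall at Screening, Week 52 and Week 104 (Appendix D) | Too late for Week 52 |

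The first three routes carry the point. It is a reasonable reading that the TA MD and Scientific Director belong to the personnel with direct oversight, but Section 5.8 does not name them.

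**4. Share of subjects still in the blinded period at unblinding.** Remaining time at a subject's Week 14 visit is 52 − 14 = 38 weeks. With uniform accrual over A weeks and a lag L from the last Week 14 visit to unblinding, the share not yet at Week 52 is (38 − L)/A. A and L are assumptions; dropout is ignored.

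- A = 52, L = 4: 34/52 = 65%, or 199 of 304
- A = 78, L = 8: 30/78 = 38%, or 117 of 304
- A = 104, L = 12: 26/104 = 25%, or 76 of 304

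**5. Sensitivity of the test (illustration only).** Assume no true effect, response p in both arms, 152 per arm, and k placebo responders turned into non-responders by decisions that were not blind. Put d = k/152, pooled rate p̄ = p − d/2, se0 = √[2p̄(1 − p̄)/152] and se1 = √{[p(1 − p) + (p − d)(1 − p + d)]/152}. The two-sided error is 1 − Φ[(1.96·se0 − d)/se1] + Φ[(−1.96·se0 − d)/se1].

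For p = 0.30 and k = 3: d = 0.0197, se0 = 0.0521, se1 = 0.0520, so the error is 0.057 + 0.010 = 0.067. Over p = 0.20 to 0.40:

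- k = 1: about 0.052
- k = 3: 0.064 to 0.072
- k = 5: 0.091 to 0.115

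**The case against.** The strongest reply is that little is left for an unblinded sponsor to influence. Sites and subjects stay blinded, the ASAS domains are patient-reported, the ASAS20 response that triggers rescue is determined at the site, and the power to stop a subject's study drug is limited to safety concerns. The documents give no frequency for any of these events. All of this stands, and it is why the risk is indirect.

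It can also be said that a firewall may exist elsewhere. The supplied SAP covers only the Remission-Withdrawal Period; the Study 2 SAP is a separate document, and the text of the Operations Manual is not available here. Section 4.1 unblinds the team for the purpose of the analysis and does not say that monitors or the medical director receive codes. So the absence of a firewall is not established. But Section 5.8 ends the blind to each subject's treatment for the conduct personnel as a group, and a firewall described elsewhere would conflict with that wording.

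Stronger readings are tempting and are not supported:

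- A reader might infer that the primary result is compromised. It is not: unblinding follows the last Week 14 visit.
- A reader might infer that the unblinded sponsor decides on rescue. Section 5.4 gives the response determination to the investigator or site staff.
- A reader might take 76 to 199 as subjects affected. It counts subjects with blinded time left under assumed accrual and lag; those whose outcome could change may be far fewer.
- A reader might call the assurance in Section 6.3 that committee communications "will not contain information that could potentially unblind the team to subject treatment assignments" pointless. It still protects every Week 14 endpoint before the lock.

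**Conclusion.** The point holds as a gap in protection for one controlled endpoint, not as evidence of bias. On the protocol's wording, sponsor conduct staff in Study 2 may hold individual assignments while some subjects are still in the placebo-controlled period that yields Week 52 ASAS40, the last controlled step for EU/EMA.

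The size of any effect is unknown. The 25% to 65% range rests on assumed accrual and lag and describes opportunity only. The error-rate illustration shows that a few altered outcomes would matter to the test; a reader might infer from it that type I error is inflated, but nothing in the documents shows that any outcome would be altered, and the nominal level remains two-sided 0.05. Confidence is high on what Sections 4.1 and 5.8 say, and lower on whether access was restricted in practice. The remedy is cheap enough to justify the change without a demonstrated bias.

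**What to change.** In Protocol Sections 4.1, 5.8 and 7.1, for Study 2:

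- Limit subject-level codes at the Week 14 lock to the statisticians and programmers who produce the analysis.
- State that sponsor staff who deal with sites or subjects, including the medical director, study management, monitoring and data management, see group-level results only and stay blinded to individual assignments until the Week 52 lock.
- Align the Study 2 SAP and the Operations Manual with this. If either already describes restricted access, bring Sections 4.1 and 5.8 into line with it.
- If the Week 14 lock has passed, document who held subject-level codes and from when, and report this with the Week 52 result.

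Separately, reconcile the earlier end-points for the site and subject blind in Section 5.8, for both studies, with the study-duration wording in Sections 4.1, 5.7 and 7.1. This is an editorial correction and does not depend on the sponsor blind.

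The cost is protocol wording and an access list, with no added visits or subjects. The downside is that subject-level narratives for the Week 14 report must be handled by existing staff who do not deal with sites.
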